15.1.5. SUPPORTIVE ANALYSIS OF PRIMARY EFFICACY ENDPOINT

Supportive analyses to the primary analysis of the primary efficacy endpoint will be performed using the ANCOVA model specified in Section 15.1.3 for the following:

15.1.5.1. Assessment of Consistency of Treatment Effect Across Region

To assess the consistency of treatment difference across region, descriptive statistics of the primary endpoint will be presented by treatment group within each region. The primary analysis of the primary efficacy endpoint will be repeated but will also include the region and treatment-by-region interaction as fixed effect. Should this interaction be statistically significant at the 0.15 level of significance, LS means and SE of each treatment group by region will be provided as well as the LS mean difference of each LYR-210 procedure against the Sham procedure and their SEs, 90% CIs, and p-values by region.

It is to be noted that should data be too sparse for at least one treatment group in at least one region (i.e., less than 5 ITT subjects for at least one treatment group in at least one region), only description statistics by region will be provided.

15.1.5.2. Assessment of Treatment Effect Across Subgroups Described in Section 7.6

To assess the consistency of treatment difference across subgroups, descriptive statistics of the primary endpoint will be presented by treatment group within each subgroup. An exploratory analysis of covariance on the CFBL of CS7DA4S score at Week 4 will be carried out on the ITT analysis set for subjects with available data. The ANCOVA model will include the baseline CS7DA4S score as a covariate, the stratification variables, and treatment group as a fixed effect and will be repeated for each subgroup of interest.

If data is too sparse for at least one treatment group in at least one subgroup (i.e., less than 5 ITT subjects for at least one treatment group in at least one subgroup), only descriptive statistics by subgroup will be provided.

15.2. SECONDARY EFFICACY

15.2.1. KEY SECONDARY EFFICACY ENDPOINTS AND DERIVATION

15.2.1.1. CFBL in CS7DA4S at Week 24

CFBL at Week 24 will be derived as described in Section 15.1.1.

15.2.1.2. Proportion of Subjects with at Least 1-point Decrease in Bilateral Zinreich Score in at Least One Pair of Anterior Ethmoid, Maxillary, Posterior Ethmoid, Frontal or Sphenoid Sinuses at Week 24

Sinus inflammation will be assessed by MRI at time points specified in the schedule of events in Section 8.1 of the protocol. The sinus inflammation will be assessed using the Zinreich modified Lund-Mackay scoring system (Likness, et al., 2014). The Zinreich score for each sinus will be assessed by Medical Metrics, Inc. (MMI) and all analysis will use the data collected by MMI. Six areas of each sinus (left and right) will be assessed:

- Anterior ethmoid
- Maxillary
- Posterior Ethmoid
- Frontal
- Sphenoid
- Ostiomeatal Complex (OMC)

Each area will be assigned a score based on the percentage of opacification as follows:

- 0=0%
- 1=1%-25%
- 2=26%-50%
- 3=51% to 75%
- 4=76% to 99%
- 5=100% or completely occluded

The OMC is given a score of 0 to 2 as follows:

- 0=completely patent
- 1=partially occluded
- 2=completely occluded

The bilateral Zinreich score for each area will be derived by [REDACTED] Biostatistics by adding the score for both sinuses together. The range of the score will be 0-10 except for OMC which will have a range of 0-4. The bilateral Zinreich score for each area will only be calculated if both sinus scores are non-missing. The total bilateral score

will be the sum of all 6 areas and will have a range of 0-54. The total bilateral score will only be calculated when all bilateral scores for each of the 6 areas are present. The baseline bilateral Zinreich score for each area and baseline total score will be the value recorded at screening. The individual and total Zinreich scores for all areas at all visits will be summarized and listed.

The key secondary endpoint will be the proportion of subjects with at least 1-point decrease from baseline in the Zinreich score in at least 1 pair of the anterior ethmoid, maxillary, posterior ethmoid, frontal or sphenoid sinuses at Week 24.

15.2.1.3. Time-to-Treatment Failure

Time-to-treatment failure, in days, will be derived as:

$$\text{Time (days)} = \text{date of treatment failure} - \text{treatment start date} + 1$$

Where treatment failure is defined as:

- after subject enrollment, the subject being recommended by treating physician for oral corticosteroid or ESS due to worsening of CS symptoms as collected on the Follow-up eCRF

OR

- the subject complaining of persistent CS symptoms, i.e., has an average CS7DA4S score over the preceding 30 days greater than or equal to the baseline CS7DA4S score as defined by ██████████ Biostatistics.
 - The earliest timepoint at which to calculate this score is Day 31. For each day post-Day 30, the average CS7DA4S over the preceding 30 days will be derived and compared to the baseline CS7DA4S score
 - The average CS7DA4S for at least 21 of the preceding 30 days should be available for this derivation.

Subjects without the event will be censored at their follow-up period. That is, should a subject reach Week 24 without having met the criteria for the time-to-treatment failure, the subject will be censored at the date of the Week 24 visit; should a subject discontinue early from the study before Week 24 without having met the criteria for the time-to-treatment failure, the subject will be censored at the date of discontinuation from study.

Time-to-treatment failure will be derived at different timepoints: Weeks 2 (15 days), 4 (29 days), 8 (57 days), 12 (85 days), 16 (113 days), 20 (141 days) and 24 (169 days). These timepoints are independent of the scheduled visits.

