#### **10.6.2 Key Secondary Efficacy Endpoint Analysis**

The key secondary endpoints are:

- CFBL in CS7DA4S score at Week 24
- Percentage of subjects with at least 1-point decrease in bilateral Zinreich score in at least one pair of the anterior ethmoid, maxillary, posterior ethmoid, frontal, or sphenoid sinuses at Week 24
- Time to treatment failure: A treatment failure is defined as, after subject enrollment, the subject being recommended by treating physician for oral corticosteroid or ESS due to worsening of CS symptoms, or the subject complaint of persistent CS symptoms with an average CS7DA4S score over the preceding 30 days greater than or equal to the Baseline CS7DA4S score.

For each key secondary endpoint, each LYR-210 dose will be compared to sham at a one-sided 0.05 level of significance. There will be no adjustment of the significance level for multiple comparisons across the secondary endpoints.

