7. STATISTICAL CONSIDERATIONS

7.1. SAMPLE SIZE

Per the null and alternative hypotheses described in Section 7.8 and under the assumption that $\mu_C = -1.30$ and $\mu_{L_{2500}}$ and/or $\mu_{L_{7500}} = -3.00$ (conservatively set, based on the mean of this endpoint for LYR-210 in Phase I study, and approximately 130% larger decrease than the assumed control mean of -1.30) and that the true standard deviation (SD) of the primary endpoint within each treatment group is at most 2.4, then an evaluable sample size of 63 subjects (21 per treatment group) yields 73% power to reject at least one null hypothesis in favor of the alternative at a one-sided 0.05 level of significance. An additional 6-9 subjects will be enrolled to account for potential subject dropout.

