15.2.4.3. Analysis of Time-to-Treatment Failure

The number and percentage of subjects with and without treatment failure will be presented based on the ITT analysis set. For subjects without treatment failure, the censoring reason will be summarized. Time-to-treatment failure (days) will be analyzed for the ITT analysis set using a Cox proportional hazards model with fixed effects for baseline CS7DA4S score, treatment group and the stratification variables (nasal allergy and nasal polyps). The Hazard ratio of each LYR-210 treatment group vs. the Sham treatment group, its 90% CI and p-values will be presented.

Additionally, Kaplan-Meier results will be displayed for the 25%, 50% and 75% quartiles, along with Kaplan-Meier estimates of probability of treatment failure at different timepoints: Weeks 2, 4, 8, 12, 16, 20 and 24. These timepoints are independent of the scheduled visits. Kaplan-Meier plots of time-to-treatment failure will be produced for each treatment group.

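### Time to treatment failure: many diary failures are likely to be tied on Day 31, no tie method is named for the Cox model, and no sensitivity analysis covers subjects whose diary becomes non-evaluable

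*SAP*

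**What the plan says.** Time to treatment failure is the third key secondary endpoint. Protocol 10.6.2 sets the test: "For each key secondary endpoint, each LYR-210 dose will be compared to sham at a one-sided 0.05 level of significance".

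Failure has two components in SAP 15.2.1.3. One is a physician's recommendation of oral steroids or sinus surgery, taken from the Follow-up eCRF. The other is a diary rule: the mean CS7DA4S over the previous 30 days is at or above baseline. On timing and evaluability of the diary rule the SAP says:

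- "The earliest timepoint at which to calculate this score is Day 31", with a check on each later day.
- "The average CS7DA4S for at least 21 of the preceding 30 days should be available for this derivation". Each daily CS7DA4S itself needs 5 of 7 daily totals (SAP 15.1.1).

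Protocol 10.6.2.3 words this component as a complaint by the subject together with the 30-day score. The SAP defines the complaint by the score alone, so the rule becomes automatic.

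On censoring at Week 24: "without having met the criteria for the time-to-treatment failure, the subject will be censored at the date of the Week 24 visit". Subjects who leave earlier are censored at study discontinuation. Neither rule mentions the last evaluable diary day, and SAP 15.2.3.1 excludes imputation for this endpoint.

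SAP 15.2.4.3 analyses the ITT set "using a Cox proportional hazards model with fixed effects for baseline CS7DA4S score, treatment group and the stratification variables". No tie method appears there or elsewhere. SAP 7.9 gives only the SAS version.

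**The concern.** There are two separate issues.

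First, a subject whose symptoms have not improved on average by the end of the first month cannot fail on the diary before Day 31, and fails on that day. The diary events of such subjects are therefore tied by construction. The methods for handling ties in a Cox model diverge when many events share one time and few subjects are at risk. Leaving the method open leaves the estimate and the p-value of a key secondary endpoint partly undefined until the program is written.

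Second, a subject who stops the diary but stays in the study can no longer meet the diary rule, yet remains in the risk set to Week 24. For that component, time that cannot be assessed is treated as failure-free. If more diaries were lost in one arm, the comparison could shift, and no planned analysis is aimed at this.

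**Working it through.** **1. The plan's own figure.** SAP 7.1 states that "an evaluable sample size of 63 subjects (21 per treatment group) yields 73% power to reject at least one null hypothesis". Inputs: difference 3.00 - 1.30 = 1.70, SD 2.4, 21 per arm, one-sided 0.05. The standard error is 2.4 x sqrt(2/21) = 0.741, and 1.70/0.741 = 2.295. The noncentral t with 40 df gives 73.0%, which matches for one dose against sham. This figure belongs to the primary endpoint. The documents give no event count, hazard ratio or power for time to treatment failure.

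**2. Expected tie on Day 31.** The Week 4 change is used as a proxy for the 30-day average, and both doses are taken at -3.0.

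- Sham: P(change >= 0) = 1 - Phi(1.3/2.4) = 0.294; x 21 = 6.2 subjects.
- Each LYR-210 arm: 1 - Phi(3.0/2.4) = 0.106; x 21 = 2.2 subjects.
- Three arms: 6.2 + 2 x 2.2 = 10.6 events on one day. With 24 per arm (63 + 9 = 72 enrolled) it is about 12.1.

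**3. Effect of the tie method on that single tie.**

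- Breslow tends to the ratio of risks: 0.106/0.294 = 0.359.
- The grouped proportional-hazards value is ln(1 - 0.106)/ln(1 - 0.294) = 0.321.
- ln(0.359)/ln(0.321) = 0.90, so Breslow keeps about 90% of the log hazard ratio.

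**4. Simulated daily diaries.** Assumptions: 23 per arm, baseline about 9, time constant of change 3-14 days, daily SD 1.0, drift SD 0.03-0.10 per day, no physician events, strata omitted, 600 trials per scenario.

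| | Breslow | Efron |
|---|---|---|
| Median HR, 7500 µg vs sham | 0.38-0.40 | 0.34-0.375 |
| Power, one-sided 5% | 37-45% | 45-52% |
| Rejection under the null | 3.2% | 5.3% |

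The mean log hazard ratio differs by about 8%, and power by about 6-9 points within scenario. Between 67% and 84% of diary events fell on Day 31; other assumed trajectories gave values as low as 63%.

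**5. When the diary becomes non-evaluable.** Applying the 5-of-7 and 21-of-30 rules day by day:

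- Seven consecutive missed days leave every window evaluable. Eight give 21 non-evaluable days, 14 give 27 and 28 give 41.
- After a permanent stop on day s, the last evaluable day is s + 12. A stop before Day 19 means the diary rule is never assessed (18 + 12 = 30, which is before Day 31).

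**6. Effect on the hazard ratio.** Simulated with 3,000 per arm, Efron ties and no physician events. The loss rates are assumed, because the documents give none.

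| Diary stopped, sham / LYR-210 | Day of stop | Complete diary | SAP rule | Follow-up ended at last evaluable day |
|---|---|---|---|---|
| 10% / 10% | 1-168 | 0.371 | 0.374 | 0.373 |
| 20% / 20% | 1-168 | 0.354 | 0.362 | 0.358 |
| 20% / 5% | 1-168 | 0.321 | 0.330 | 0.319 |
| 5% / 20% | 1-168 | 0.352 | 0.338 | 0.351 |
| 10% / 10% | 1-18 | 0.349 | 0.365 | 0.359 |
| 20% / 5% | 1-18 | 0.360 | 0.458 | 0.365 |
| 5% / 20% | 1-18 | 0.336 | 0.286 | 0.343 |

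The shift from complete data is below 0.02 except when loss is both early and unequal. The direction then depends on which arm loses more diaries.

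**7. A censoring change that does not work.** Suppose only event-free subjects were censored at their last evaluable diary day, while later physician events still counted. With physician events only, a true hazard ratio of 1.0, 15-30% event risk and 20%/5% non-evaluable diaries (all assumed), the SAP rule gave 0.98-1.01. The altered rule gave 0.84-0.89, a false effect in favour of LYR-210.

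**The case against.** Several points on the other side stand.

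- Failure is a composite. Subjects are contacted at least every four weeks in the treatment stage (Protocol 4.1.2, apart from the two-week visit early on), so physician recommendations are captured without a diary. Keeping such a subject at risk is correct for that component.
- Protocol 10.6.2.3 already prescribes no imputation and censoring at the end of follow-up. The SAP implements this.
- The per-protocol set requires a Week 4 CS7DA4S (SAP 5.6), that is, 5 of Days 23-29, so it drops anyone who stops the diary before Day 27. Protocol 10.6.2.3 repeats the analysis in that set, although SAP 15.2.4.3 names only ITT. This helps in part, but the set also excludes subjects for unrelated reasons, so it does not isolate diary loss.
- The tie effect is small against the precision. With 6 and 2 events the standard error of the log hazard ratio is about sqrt(1/6 + 1/2) = 0.82, while the shift is about ln(0.359/0.321) = 0.11. It also errs on the conservative side. This is fair for the estimate, but the undersized test (3.2%) adds to the loss of power.
- SAP 7.8 calls the study exploratory and provides nominal p-values only.

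A reader might go further and infer that the software default will be Breslow, so that the hazard ratio is biased by construction. The documents name the SAS version and no tie option, so they support only that the method is unspecified. A reader might also infer that missing diaries are scored outright as success and that the main censoring date should move. The physician component contradicts the first part, and step 7 of the working contradicts the obvious form of the second. That form also has no censoring date for a subject who never has an evaluable window.

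**Conclusion.** The point holds in two limited parts.

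The tie method should be named. That Day 31 is the first possible diary failure is in the SAP text. The heavy tie is a projection from the plan's means and SD, with Week 4 change as a proxy. The cost of Breslow, an 8-10% smaller log hazard ratio and about 6-9 points of power, is relative to Efron and rests on assumed diary trajectories without physician events.

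A missing-diary sensitivity analysis is lacking. The censoring rule does treat non-evaluable diary time as free of diary failure, but the harm is material only if loss is early and unequal. The 20%/5% split is an assumption used to show the range, and nothing in the documents predicts it.

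Neither part affects the primary endpoint or its 73% power. Both are worth settling before unblinding because they concern a key secondary endpoint in a small trial.

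**What to change.** - **SAP 15.2.4.3:** state that the Cox model uses Efron ties, or the exact likelihood for continuous time. Do not use the discrete logistic option as a substitute: it targets an odds ratio, which for the Day 31 tie would be (0.106/0.894)/(0.294/0.706) = 0.284. This costs one sentence.
- **SAP 15.2.1.3:** keep the current censoring rule for the main analysis.
- **Add one sensitivity analysis:** end follow-up at the last evaluable diary day for every subject, with or without an event, and at the latest at the Week 24 visit. Determine that day from diary availability alone and do not count events after it. State in advance how subjects who never have an evaluable window are handled, and report their number by arm.
- **Do not** adopt a rule that moves the censoring date for event-free subjects only.

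The cost is one extra run. Some late physician-recommended failures are lost, but only in the sensitivity analysis.

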15.2.2. OTHER SECONDARY EFFICACY ENDPOINTS AND DERIVATIONS

15.2.2.1. Time-to-Onset of Action

Onset of action is defined as, within the first 30 days of treatment, the time when all subsequent mean CFBL in the

CS7DA4S score of the LYR-210 is statistically significantly greater than that for the Sham procedure.

For this endpoint, the CS7DA4S will be calculated daily from Days 8 to 30. That is, the CS7DA4S at Day 8 will be the average of the total daily scores for the 4 CS cardinal symptoms over Days 2 to 8, the CS7DA4S at Day 9 will be the average of the total daily scores for the 4 CS cardinal symptoms over Days 3 to 9, and so on up to Day 30 which will be the average of the total daily scores for the 4 CS cardinal symptoms over Days 24 to 30.

Then, the CFBL to each of these daily CS7DA4S values will be calculated.

15.2.2.2. CFBL in CS7DA4S and 7-day Average Score of Individual Symptoms at Additional Timepoints

CFBL in CS7DA4S will be derived for Weeks 8, 12, 16 and 20 as per Section 6.7.

In addition, the 7-average score of each individual symptom will be calculated at each visit only if at least 5 of the previous 7 days have available scores. Then, the CFBL in the 7-day average score of each individual cardinal CS symptom score will be calculated for Weeks 1, 2, 3, 4, 8, 12, 16, 20 and 24 as per Section 6.7.

15.2.2.3. 22-Item Sino-Nasal Outcome Test (SNOT-22) Questionnaire

SNOT-22 questionnaire data will be collected in ePRO. Subjects score the severity of their symptoms and social/emotional consequences of CS over the past two weeks on a 6-point scale:

- 0=no problem
- 1=very mild problem
- 2=mild or slight problem
- 3=moderate problem
- 4=severe problem
- 5=problem as bad as it can be

The scores are summed within each domain as per [Table 3: Categorized Survey Items for Separate Domains of the SNOT-22 Instrument](#) (DeConde, Bodner, Mace, & Smith, 2014), where higher scores indicate a higher severity of symptoms or social/emotional consequences of CS. For each domain, if less than 50% of the domain items are missing at a visit for a subject, the missing items will be imputed with the mean of subject's non-missing items at that visit prior to the domain score calculation. Otherwise if 50% or more of a domain items are missing at a visit for a subject, the subject's domain score will be set to missing at that visit.

Table 3: Categorized Survey Items for Separate Domains of the SNOT-22 Instrument

SNOT-22 Domains	Survey Items	Score Range
Rhinologic Symptoms	#1, #2, #3, #4, #7, #12	0–30
Extra-Nasal Rhinologic Symptoms	#5, #6, #7	0–15
Ear/Facial Symptoms	#3, #8, #9, #10, #11	0–25
Psychological Dysfunction	#16, #17, #18, #19, #20, #21, #22	0–35
Sleep Dysfunction	#13, #14, #15, #16, #17	0–25

The total SNOT-22 score will also be calculated as the sum of all 22 questions and will have a range of 0-110. For the total score, if less than 50% of the items are missing at a visit for a subject, the missing items will be imputed with the mean of the subject’s non-missing items at that visit prior to the total score calculation. Otherwise if 50% or more of the questionnaire items are missing at a visit for a subject, the total score will be set to missing at that visit for that subject.

CFBL in the total and subdomain SNOT-22 scores will be derived for Weeks 2, 4, 8, 12, 16, 20 and 24 as per Section 6.7. If a subject’s CFBL in total SNOT-22 score is greater than 8.9 (i.e. the score decreased by more than 8.9), the subject is considered to have achieved a minimally important clinical difference.

15.2.2.4. Change from Baseline in Bilateral Zinreich Anterior Ethmoid, Maxillary, Posterior Ethmoid, Frontal, Sphenoid and OMC Sinus Scores, and Total Score at Week 24

The bilateral Zinreich anterior ethmoid, maxillary, posterior ethmoid, frontal, and sphenoid scores at Week 24 will be calculated as defined in Section 15.2.1.2. The bilateral Zinreich OMC and total Zinreich scores will also be calculated as defined in Section 15.2.1.2.

Then, the CFBL in each of these endpoints will be calculated at Week 24 as per Section 6.7.

15.2.2.5. 36-Item Short Form Health Survey Version 2 (SF-36v2) Questionnaire

The SF-36v2 questionnaire is a multi-purpose, short-form health survey with 36 questions/items. It yields 8 functional health and well-being domains as well as 2 psychometrically-based physical and mental overall component summary measures, where lower scores imply higher disability (i.e., a score of zero is equivalent to maximum disability and a score of 100 is equivalent to no disability).

The 8 domains of the SF-36 are (refer to Table 4: SF-36v2® Health Survey Measurement Model):

- Physical Functioning (PF)
- Role-Physical (RP)
- Bodily Pain (BP)
- General Health (GH)

- Vitality (VT)
- Social Functioning (SF)
- Role-Emotional (RE)
- Mental Health (MH)

The two overall component summary measures are (refer to [Table 4: SF-36v2® Health Survey Measurement Model](#)):

- Physical Component Summary (PCS)
- Mental Component Summary (MCS)

Table 4: SF-36v2® Health Survey Measurement Model

SF-36v2 Components and Domains	Survey Items
Physical Component Summary (PCS)	
Physical Functioning (PF)	#3a, #3b, #3c, #3d, #3e, #3f, #3g, #3h, #3i, #3j
Role -Physical (RP)	#4a, #4b, #4c, #4d
Bodily Pain (BP)	#7, #8
General Health (GH)	#1, #11a, #11b, #11c, #11d
Mental Component Summary (MCS)	
Vitality (VT)	#9a, #9e, #9g, #9i
Social Functioning (SF)	#6, #10
Role-Emotional (RE)	#5a, #5b, #5c
Mental Health (MH)	#9b, #9c, #9d, #9f, #9h

There is also a single item (item #2) that assesses health transition, which is not included in the scoring of the scales and overall component summary measures. Scoring will be performed with the Optum™ software as follows:

- First, 10 items are reverse-coded (Questions #1, #6, #7, #8, #9a, #9d, #9e, #9h, #11b and #11d) to ensure that across all questions, a higher score will indicate a better health state. An algorithm for an algebraic summation of the item scores is applied to produce domain-specific raw scale scores that account for missing item responses i.e., when calculating the raw domain scores, if at least half the item scores for a domain are non-missing, the missing item scores are replaced by the average of the non-missing item scores for the domain before applying the algorithm for an algebraic summation. Otherwise if 50% or more of the item scores for a domain are missing, the raw domain score is set to missing.
- Domain-specific raw scale scores are then transformed to a 0 to 100 range, after which a norm-based (T-score) transformation is applied so that each scale ranges from 0 to 100, with a mean of 50 and a standard

deviation of 10. The norm-based transformation is applied so that domain-specific scale scores can be meaningfully compared between each other.

The PCS and MCS are computed by aggregating domain scores using factor score coefficients. The aggregated component summary scores are also standardized to have a mean of 50 with a standard deviation of 10.

The Eight domain scores and the two summary scores will be calculated using software provided by the publisher, Optum™. The CFBL in the 8 domains and 2 overall component summary measures will be calculated at each visit as per Section 6.7.

